Study to Evaluate the Safety and Efficacy of ARCR	REGENETEN.2020.01
augmented with REGENETEN™ Bioinductive Implant	Version: 2.0, 08 Dec
System in Full-thickness Tears (large or massive) Repair	2021
versus ARCR alone	Page: 10 of 134

versus Altolt alone	1			
	 Subjective shoulder value (SSV), 			
	○ EuroQol 5 Dimension 5 Level (EQ-5D-5L) Score,			
	 Patient satisfaction Questionnaire, 			
	○ Pain, Visual analog scale (VAS) Score (additionally at			
	baseline, 2 weeks, 6 weeks, 3 months and 6 months);			
	MRI Tendon Findings in ARCR augmented with			
	REGENETEN versus ARCR alone postoperatively at			
	Baseline, 3, 6, 12 and 24 months including			
	○ Sugaya score,			
	o Goutallier grading,			
	 Total tendon thickness, tendon length, 			
	○ Size of retear (anteroposterior [AP]/mediolateral			
	[ML]),			
	○ Shape of retear;			
	Outcome of Return to Work Questionnaire in ARCR			
	augmented with REGENETEN versus ARCR alone			
	(additionally at 2 and 6 weeks);			
	Cumulative duration of opioid use in ARCR augmented with			
	REGENETEN versus ARCR alone at 2 weeks			
	postoperatively;			
	Total operative time ARCR augmented with REGENETEN			
	versus ARCR alone;			
	 Sling type and mobilization time in ARCR augmented with REGENETEN versus ARCR alone. 			
Other Exploratory Endpoint(s):	To assess safety and efficacy as summarized in secondary			
	endpoints in at-risk groups (diabetics, smokers, hypertensive,			

Study Protocol	Smith-Nephew
A Prospective, Multi-center, Randomized Controlled	Number:
Study to Evaluate the Safety and Efficacy of ARCR	REGENETEN.2020.01
augmented with REGENETEN™ Bioinductive Implant	Version: 2.0, 08 Dec
System in Full-thickness Tears (large or massive) Repair	2021
	Page: 11 of 134

	heavy laborer, age > 65 years) after full-thickness ARCR augmented with REGENETEN versus ARCR alone; • To assess safety and efficacy as summarized in secondary endpoints in revision repair subject group after full-thickness ARCR augmented with REGENETEN;					
	 To collect health economic evidence in ARCR augmented with REGENETEN versus ARCR alone: 					
	 Aggregate health care utilization costs, 					
	 Number of unscheduled visits, 					
	 Reoperation rate, 					
	 Surgeon recommendation for reoperation, type of surgery, 					
	 Time of operation to time of retear, 					
	 Level of service (LOS): In the case of reoperation: How many nights did the subject spend in the hospital as a result of surgery? 0, 1, 2, 3, 4, 5, >5. 					

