8.3.2 Secondary Endpoints

The secondary study endpoints are:

- The cumulative 3, 12, and 24 months retear rate after full-thickness ARCR augmented with REGENETEN (confirmed on MRI) versus ARCR alone;
- Overall performance of full-thickness ARCR augmented with REGENETEN versus ARCR alone at Baseline and at 3, 6, 12 and 24 months assessed by:
 - Oxford Shoulder Score (OSS),
 - Western Ontario Rotator Cuff (WORC)/Chinese version WORC (C-WORC) Index,
 - Constant-Murley Score,
 - Subjective shoulder value (SSV),
 - o EuroQol 5 Dimension 5 Level (EQ-5D-5L) Score,
 - Patient satisfaction Questionnaire,
 - Pain, Visual analog scale (VAS) Score (additionally at baseline, 2 weeks, 6 weeks, 3 months and 6 months);
- MRI Tendon Findings in ARCR augmented with REGENETEN versus ARCR alone postoperatively at Baseline, 3, 6, 12 and 24 months including:
 - Sugaya score,

CONFIDENTIAL AND PROPRIETARY

Study Protocol	Smith-Nephew
A Prospective, Multi-center, Randomized Controlled	Number:
Study to Evaluate the Safety and Efficacy of ARCR	REGENETEN.2020.01
augmented with REGENETEN™ Bioinductive Implant	Version: 2, 08 Dec 2021
System in Full-thickness Tears (large or massive) Repair versus ARCR alone	Page: 49 of 134

- Goutallier grading,
- o Total tendon thickness, tendon length,
- Size of retear (anteroposterior [AP]/mediolateral [ML]),
- Shape of retear;
- Outcome of Return to Work Questionnaire in ARCR augmented with REGENETEN versus ARCR alone (additionally at 2 and 6 weeks);
- Cumulative duration of opioid use in ARCR augmented with REGENETEN versus ARCR alone at 2 weeks postoperatively;
- Total operative time in ARCR augmented with REGENETEN versus ARCR alone;
- Sling type and mobilization time in ARCR augmented with REGENETEN versus ARCR alone.

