9.1.7 Postoperative Follow-Up Visit 6 (6 Months [182 ± 30 days])

- 1. Query subject regarding any changes in general health and the use of concomitant medications. If any AEs, ADEs or DDs are observed or reported, they must be recorded as instructed in Section 12 Adverse Events and Device Deficiencies.
- 2. Have the subject complete VAS pain score.
- 3. Complete the Constant-Murley Questionnaire (Physician/Examiner completed portion).
- 4. Have the subject complete the OSS Questionnaire.
- 5. Have the subject complete the WOR/C-WORC Questionnaire.
- 6. Have the subject complete the subjective part of Constant-Murley Questionnaire.
- 7. Have the subject complete the SSV Questionnaire.
- 8. Have the subject complete the EQ-5D-5L Questionnaire.
- 9. Have the subject complete Patient satisfaction Questionnaire.
- Have the subject complete the Return to Work Questionnaire (if appropriate).
- Complete MRI assessment.
- 12. If any Reoperation occurred complete reoperation CRF.
- 13. Complete End of Study/exit information (if appropriate)
- 14. Instruct the subject on follow-up procedures, including returning the treatment facility for follow-up at Visit 7 at 12 months (365 ± 60 days).

CONFIDENTIAL AND PROPRIETARY

Study Protocol	Smith-Nephew
A Prospective, Multi-center, Randomized Controlled	Number:
Study to Evaluate the Safety and Efficacy of ARCR	REGENETEN.2020.01
augmented with REGENETEN™ Bioinductive Implant	Version: 2.0, 08 Dec
System in Full-thickness Tears (large or massive) Repair	2021
	Page: 59 of 134

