9.1.8 Postoperative Follow-Up Visit 7 (12 Months [365 ± 60 days])

- 1. Query subject regarding any changes in general health and the use of concomitant medications. If any AEs, ADEs or DDs are observed or reported, they must be recorded as instructed in Section 12 Adverse Events and Device Deficiencies.
- 2. Complete the Constant-Murley Questionnaire (Physician/Examiner completed portion).
- 3. Have the subject complete the OSS Questionnaire.
- 4. Have the subject complete the WOR/C-WORC Questionnaire.
- 5. Have the subject complete the subjective part of Constant-Murley Questionnaire.
- 6. Have the subject complete the SSV Questionnaire.
- 7. Have the subject complete the EQ-5D-5L Questionnaire.
- 8. Have the subject complete Patient satisfaction Questionnaire.
- 9. Have the subject complete the Return to Work Questionnaire (if appropriate).
- 10. Complete MRI assessment.
- 11. If any Reoperation occurred complete reoperation CRF.
- 12. Complete End of Study/exit information (if appropriate).
- 13. Instruct the subject on follow-up procedures, including returning the treatment facility for follow-up at Visit 8 at 24 months (730 ± 60 days).

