9.1.9 Postoperative Follow-Up Visit 8 (24 Months [730 ± 60 days])

- 1. Query subject regarding any changes in general health and the use of concomitant medications. If any AEs, ADEs or DDs are observed or reported, they must be recorded as instructed in Section 12 Adverse Events and Device Deficiencies.
- 2. Complete the Constant-Murley Questionnaire (Physician/Examiner completed portion).
- 3. Have the subject complete the OSS Questionnaire.
- 4. Have the subject complete the WOR/C-WORC Questionnaire.
- 5. Have the subject complete the subjective part of Constant-Murley Questionnaire.
- 6. Have the subject complete the SSV Questionnaire.

CONFIDENTIAL AND PROPRIETARY

Study Protocol	Smith-Nephew
A Prospective, Multi-center, Randomized Controlled	Number:
Study to Evaluate the Safety and Efficacy of ARCR	REGENETEN.2020.01
augmented with REGENETEN™ Bioinductive Implant	Version: 2.0, 08 Dec
System in Full-thickness Tears (large or massive) Repair	2021
versus ARCR alone	Page: 60 of 134

- 7. Have the subject complete the EQ-5D-5L Questionnaire.
- 8. Have the subject complete Patient satisfaction Questionnaire.
- 9. Have the subject complete the Return to Work Questionnaire (if appropriate).
- Complete MRI assessment.
- 11. If any Reoperation occurred complete reoperation CRF.
- 12. Complete Exit Visit CRF and inform subject of End of Study.

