10.4.2 Analysis of Secondary Endpoints

The following secondary endpoints will be analyzed for this study:

- Retear rate at 3, 12 and 24 months post-operative will be summarized and presented as per the Primary Endpoint analysis.
- OSS, WORC/C-WORC, Constant, SSV and EQ-5D-5L PRO scores will be calculated and summarized for each visit using descriptive statistics for continuous variables, separately for the ARCR augmented with REGENETEN group and the ARCR alone (standard of care) group. Changes from baseline to each subsequent follow up visit will be similarly summarized. Repeated measures ANCOVA models will be used to assess statistical significance in the change from baseline to each time point. The null hypothesis will be that there is no difference between baseline and the respective time point. An estimate of the LS mean difference between the time points for the scores will be reported, along with the corresponding 95% confidence interval and p-value. A separate model will be used to assess statistical significance between the treatment groups at each time point. Minimal Clinically Important Differences will be assessed and presented where appropriate.
- Patient satisfaction and return to work questionnaire will be presented as number and percentage of patients who have selected each of the responses at each time point. The duration a patient has taken away from work will be summarized descriptively.
- VAS Pain score (1-100mm) will be summarized at baseline, 2 and 6 weeks, 3, 6, 12 and 24 months using descriptive statistics for continuous variables. Change from baseline to each follow up assessment will be similarly summarized and p-values will be presented.

CONFIDENTIAL AND PROPRIETARY

Study Protocol	Smith-Nephew
A Prospective, Multi-center, Randomized Controlled	Number:
Study to Evaluate the Safety and Efficacy of ARCR	REGENETEN.2020.01
augmented with REGENETEN™ Bioinductive Implant	Version: 2.0, 08 Dec
System in Full-thickness Tears (large or massive) Repair	2021
	Page: 73 of 134

- MRI analysis will be conducted by an external vendor at baseline, 3, 6, 12 and 24 months and will be presented appropriately for continuous or categorical variables.
- Opioid use will be collected each day for 2 weeks following surgery. The number of days
 of opioid use will be calculated for each patient and this will be presented descriptively for
 all patients, by treatment type (ARCR augmented with REGENETEN or ARCR alone).

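### VAS pain is to be analysed at 12 and 24 months, but the visit lists for 12 and 24 months contain no step to collect it

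*Combined protocol and SAP*

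**What the plan says.** **Analysis.** Section 10.4.2: "VAS Pain score (1-100mm) will be summarized at baseline, 2 and 6 weeks, 3, 6, 12 and 24 months". The next sentence extends the change-from-baseline summary and p-values to every follow-up assessment.

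**Endpoint.** The stem in section 8.3.2 reads "Overall performance of full-thickness ARCR augmented with REGENETEN versus ARCR alone at Baseline and at 3, 6, 12 and 24 months assessed by", and VAS pain is one of the measures listed under it. The VAS item itself reads "Pain, Visual analog scale (VAS) Score (additionally at baseline, 2 weeks, 6 weeks, 3 months and 6 months". The synopsis uses the same wording, beginning "Pain, Visual analog scale (VAS) Score (additionally at".

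**Collection.** Section 9.1.7 (6 months) has as its second step "2. Have the subject complete VAS pain score". The 2-week, 6-week and 3-month lists have the same step in the same position, and the baseline list has a VAS pain questionnaire as step 14. In section 9.1.8 (12 months) the second step is instead "2. Complete the Constant-Murley Questionnaire (Physician/Examiner completed portion", and VAS pain appears nowhere in the list. Section 9.1.9 (24 months) is the same in both respects.

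**The concern.** The analysis section relies on measurements that the visit procedures do not ask sites to take. Long-term pain is a named secondary outcome in a 24-month trial, and 12 and 24 months are the only VAS analyses planned beyond 6 months. A patient's pain rating on the day cannot be reconstructed later. Section 10 requires the SAP to be final only before database lock, so settling the point there would come too late for any visit already held without the questionnaire. The gap also carries into the revision-repair and at-risk group summaries, because section 10.4.3 presents these in the same way as the secondary endpoints.

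**Working it through.** The check compares the analysis times in 10.4.2 with the visit lists in 9.1.2 to 9.1.9. There is no published figure to reproduce; the arithmetic is a count.

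| Time | Analysis planned (10.4.2) | VAS step in visit list | Steps in list |
|---|---|---|---|
| Baseline (9.1.2) | yes | yes, step 14 | 15 |
| 2 weeks (9.1.4) | yes | yes, step 2 | 7 |
| 6 weeks (9.1.5) | yes | yes, step 2 | 6 |
| 3 months (9.1.6) | yes | yes, step 2 | 14 |
| 6 months (9.1.7) | yes | yes, step 2 | 14 |
| 12 months (9.1.8) | yes | **no** | 13 |
| 24 months (9.1.9) | yes | **no** | 12 |

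**Count.** Follow-up analyses planned: 6. With a collection step: 4. Without: 6 − 4 = 2, and 2/6 = 33.3%. Including baseline, 7 times are planned and 5 have a step.

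**Is a line missing from the text?** No. The 12-month list ends at "13. Instruct the subject on follow-up procedures, including returning the treatment facility for follow-up at Visit 8 at 24 months". It matches the 6-month list step for step apart from VAS: 14 − 1 = 13. The 24-month list ends at "12. Complete Exit Visit CRF and inform subject of End of Study". It also lacks VAS, and one exit step replaces the two closing steps of the 6-month list: 14 − 1 − 2 + 1 = 12. Every other 6-month assessment (Constant-Murley, OSS, WORC, SSV, EQ-5D-5L, satisfaction, return to work, MRI, reoperation) appears in both lists.

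**Does the endpoint text settle it?** No. The stem includes 12 and 24 months. The *additionally* list names five visits and stops at 6 months. Three of the five (baseline, 3 and 6 months) are already in the stem, so only 5 − 3 = 2 (2 and 6 weeks) are additional. Read literally, VAS is due at the stem visits plus 2 and 6 weeks, which agrees with 10.4.2. Read as a complete VAS schedule, it ends at 6 months, which agrees with the visit lists.

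**Does the schedule table settle it?** The 12- and 24-month columns of Table 9.1.1-1 and of the synopsis schedule are cut off in the text available for review, so they cannot be called blank. If they mark VAS, they contradict 9.1.8 and 9.1.9. If they do not, they contradict 10.4.2. A conflict remains either way.

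**The case against.** The strongest reply is that VAS was meant to end at 6 months and that 10.4.2 is simply too broad. The amendment tables in 21.1.2 and 21.1.4 give some support. Version 2.0 revisited VAS collection, added it at baseline, 3 and 6 months to correct an omission, and described the revised frequency as those visits plus 2 and 6 weeks. On that reading no intended data are lost and the fault is loose wording. This stands as evidence of intent but is not conclusive. The version 1.0 wording quoted in 21.1.4 named only 2 and 6 weeks as additional, under a stem that already covered 12 and 24 months.

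Three further points can be made:

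- **Unseen sources.** Section 9.1.1 refers sites to the schedule table for required procedures. Its late columns and the eCRF were not available, so sites may be told to collect VAS after all. This limits what can be said about data loss, but it does not remove the conflict in the text.
- **Other pain measures.** The 12- and 24-month visits still include the Constant-Murley pain item (0–15), EQ-5D-5L pain/discomfort, the satisfaction question on pain relief, the OSS and the WORC physical-symptoms domain. Long-term pain can therefore be described. None of these supplies a change from baseline on the 0–100 VAS of section 9.2.7.
- **Limited weight.** This is one secondary measure among many. That is why the point is a recommended correction and not a threat to the trial's main conclusion.

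**Conclusion.** The concern holds. Sections 10.4.2 and 9.1.8–9.1.9 disagree, and the disagreement remains whichever intent is correct. At risk are 2 of 6 planned follow-up VAS time points (33%), assuming that sites work from the itemised lists and that VAS was intended after 6 months. If it was not, the consequence is an analysis plan that promises results the trial never meant to collect. The mismatch in the text is certain; the loss of data is not. No number of affected subjects is given, because section 7.4 lets the sponsor change enrolment and the documents state no loss rate. The primary retear endpoint, the sample size and the alpha are untouched.

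**What to change.** Decide whether VAS pain continues after 6 months, then make every section agree.

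1. **If it continues:** add the VAS pain step to 9.1.8 and 9.1.9, and check that Table 9.1.1-1, the synopsis schedule and the eCRF show it at both visits. The cost is one short questionnaire at two existing visits and a small amendment.
2. **If it ends at 6 months:** limit the VAS entry in 8.3.2, the synopsis and 10.4.2 to 6 months, and check that the schedule tables and eCRF show no later VAS. This adds no subject burden, but it removes two time points from a named secondary endpoint.

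Under either option, reword the *additionally* list in 8.3.2 and the synopsis to name only 2 and 6 weeks. If VAS ends at 6 months, the VAS entry must also be taken out of the stem's 12- and 24-month coverage. The same edit can correct the scale in 10.4.2, which starts at 1, whereas section 9.2.7 defines it from 0 to 100.

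Both options need an amendment approved under section 15. The documents do not say whether any subject has reached 12 months. If some have, option 1 recovers only later visits, so the decision should be made promptly.

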10.4.3 Analysis of Other Endpoints

A logistic regression model will be used to evaluate retear rates in at-risk groups at each time point. The following binary variables will be created and included in the final model:

- Age (>65 years vs ≤65 years)
- Diabetic status (diabetic vs not diabetic)
- Smoking status (smoker vs non-smoker)
- Blood pressure (hypertensive vs not hypertensive)
- Job role (heavy laborer vs not heavy laborer)

The safety and efficacy in the revision repair subject group and at-risk groups will be summarized and presented as per the Secondary Endpoint analysis.

The following health economic evidence endpoints will be analyzed for this study:

- Aggregate health care utilization costs;
- Number of unscheduled visits;
- o Reoperation rate;

CONFIDENTIAL AND PROPRIETARY

Study Protocol	Smith-Nephew
A Prospective, Multi-center, Randomized Controlled	Number:
Study to Evaluate the Safety and Efficacy of ARCR	REGENETEN.2020.01
augmented with REGENETEN™ Bioinductive Implant	Version: 2.0, 08 Dec
System in Full-thickness Tears (large or massive) Repair	2021
versus ARCR alone	Page: 74 of 134

- Surgeon recommendation for reoperation, type of surgery;
- Time of operation to time of retear;
- Level of service (LOS): In the case of reoperation: How many nights did the subject spend in the hospital as a result of surgery? 0, 1, 2, 3, 4, 5, >5

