5.3 OTHER OBJECTIVE(S)

To assess safety and efficacy of full-thickness ARCR augmented with REGENETEN versus ARCR alone in at-risk-groups (diabetics, smokers, hypertensive, heavy laborer, age > 65 years);

To assess safety and efficacy of full-thickness ARCR augmented with REGENETEN in revision repair group (observational);

To generate health economic evidence.

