8.3.3 Other Endpoints

Other Study Endpoints are:

- To assess safety and efficacy as summarized in secondary endpoints in at-risk groups (diabetics, smokers, hypertensive, heavy laborer, age > 65 years) after full-thickness ARCR augmented with REGENETEN versus ARCR alone;
- To assess safety and efficacy as summarized in secondary endpoints in revision repair subjects group after full-thickness ARCR augmented with REGENETEN;
- To collect health economic evidence in ARCR augmented with REGENETEN versus ARCR alone:
 - Aggregate health care utilization costs,
 - Number of unscheduled visits,
 - Reoperation rate,
 - Reoperation type, type of surgery,
 - Time of baseline operation to time of reoperation,
 - Level of service (LOS): In the case of reoperation: How many nights did the subject spend in the hospital as a result of the surgery? 0, 1, 2, 3, 4, 5, >5.

CONFIDENTIAL AND PROPRIETARY

Study Protocol	Smith-Nephew
A Prospective, Multi-center, Randomized Controlled	Number:
Study to Evaluate the Safety and Efficacy of ARCR	REGENETEN.2020.01
augmented with REGENETEN™ Bioinductive Implant	Version: 2, 08 Dec 2021
System in Full-thickness Tears (large or massive) Repair versus ARCR alone	Page: 50 of 134

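### The at-risk-group logistic model (10.4.3) names five risk factors but no treatment term or treatment-by-factor interaction; fitted as listed, it gives no device-versus-control estimate in at-risk groups

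*Combined protocol and SAP*

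**What the plan says.** Section 5.3 (Other Objectives) sets a comparative aim: "To assess safety and efficacy of full-thickness ARCR augmented with REGENETEN versus ARCR alone in at-risk-groups". It names diabetics, smokers, hypertensives, heavy laborers and subjects over 65. Section 8.3.3 repeats the comparison in the matching endpoint: "heavy laborer, age > 65 years) after full-thickness ARCR augmented with REGENETEN versus ARCR alone".

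Section 10.4.3 gives two routes to this objective.

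- **A model for retear.** "A logistic regression model will be used to evaluate retear rates in at-risk groups at each time point". The next sentence reads "The following binary variables will be created and included in the final model", followed by age, diabetic status, smoking status, blood pressure and job role, each dichotomized. Treatment arm is not in the list, and neither is any interaction. No analysis population is named for this model.
- **Summaries.** "The safety and efficacy in the revision repair subject group and at-risk groups will be summarized and presented as per the Secondary Endpoint analysis". The secondary analysis in 10.4.2 compares arms. For retear: "Retear rate at 3, 12 and 24 months post-operative will be summarized and presented as per the Primary Endpoint analysis". For the patient-reported scores: "A separate model will be used to assess statistical significance between the treatment groups at each time point".

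**The concern.** The objective is a contrast between arms within groups. The variables listed for the model describe the groups only. A model with those terms says whether, for example, diabetics retear more often than non-diabetics with both arms mixed together. It does not say whether the device reduces retear in diabetics. Adding a single treatment term would not settle it either: that gives one common effect across all subjects, not an effect within each group.

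At stake is an exploratory objective, not the primary conclusion. However, retear at 6 months is the trial's main outcome, and in the at-risk groups it is the one retear time point for which no between-arm analysis is clearly specified. The study is not blinded (8.2.2), and the statistical analysis plan need only be final before database lock (section 10). There is therefore some value in fixing the terms early.

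**Working it through.** The documents state no sample size, power or effect for the at-risk analysis, so there is no figure to reproduce. The check has three parts.

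**1. What each route delivers**

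| Needed | Logistic model as listed | Summaries as in 10.4.2 |
|---|---|---|
| Device vs control on retear in the group, 3, 12, 24 months | No | Yes, following the primary analysis |
| The same at 6 months | No | Not listed; 6-month Sugaya findings are presented descriptively |
| Device vs control on patient-reported scores in the group | Not applicable | Yes |
| Whether the effect differs by factor | No | No |

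**2. What the five-factor model estimates**

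Inputs: retear 30% on control and 15% on device (section 11), 1:1 allocation (8.4.2). The device odds ratio is (0.15/0.85)/(0.30/0.70) = 0.41. Suppose diabetes itself has no effect on retear. Pooled over equal arms, the retear rate is (30% + 15%)/2 = 22.5% where the device works and 30% where it does not. The odds are 0.225/0.775 = 0.290 and 0.30/0.70 = 0.429. The odds ratio for diabetic against non-diabetic is then:

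- device works equally in everyone: 0.290/0.290 = 1.00;
- device does nothing: 0.429/0.429 = 1.00;
- device works only in non-diabetics: 0.429/0.290 = 1.48;
- device works only in diabetics: 0.290/0.429 = 0.68.

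A simulation of 200,000 subjects with all five factors gave 0.99, 1.02, 1.47 and 0.68. The first two cases cannot be told apart. Nor is 1.48 evidence about the device: it would also arise if the device did nothing and retear were simply 30% in diabetics and 22.5% in the rest. When treatment and treatment-by-diabetes were added to the same simulated data, the within-diabetic device odds ratio was recovered: 0.40 to 0.42 where the truth was 0.41, and 0.96 to 1.02 where it was 1.0.

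**3. Precision once the terms are added**

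Assumptions: factor prevalence 10% to 50% (not in the documents), all 130 per arm evaluable, 30% vs 15% in every level, two-sided 5% (10.1). With n per arm in the group:

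- half-width of the risk difference = 1.96 × √[(0.30×0.70 + 0.15×0.85)/n] = 1.96 × √(0.3375/n);
- standard error of the log ratio of odds ratios = √[(1/n + 1/(130−n)) × (1/0.21 + 1/0.1275)]; the ratio detectable with 80% power is exp(2.80 × SE).

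| Prevalence | n per arm | Power in group | Half-width (points) | Detectable ratio of odds ratios |
|---|---|---|---|---|
| 10% | 13 | 14% | 32 | 18.3 |
| 20% | 26 | 25% | 22 | 8.9 |
| 30% | 39 | 35% | 18 | 6.7 |
| 40% | 52 | 45% | 16 | 5.9 |
| 50% | 65 | 54% | 14 | 5.7 |

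For example, at n = 26: 1.96 × √(0.3375/26) = 0.223.

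**The case against.** Four points can be made for the plan.

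- **The list is not said to be exhaustive.** A reader might infer that the model contains the five factors and nothing else. The text does not say so: it lists variables to be derived, and arm needs no derivation. The primary model in 10.4.1 does not name treatment either, yet it plainly serves a between-arm hypothesis, and section 10 calls itself a brief description. This stands: omission from the list is not proof of exclusion. It goes only so far, because 10.4.1 states a between-arm hypothesis from which treatment follows and 10.4.3 states none. Even if treatment is presumed, interactions cannot be.
- **There is a second route.** The summaries compare arms, so it would be wrong to infer that the objective has no analysis at all. This stands for 3, 12 and 24 months and for the patient-reported scores. Section 8.3.3 defines the at-risk endpoint through the secondary endpoints, which explains why 6-month retear is missing there. Six-month Sugaya grades are a secondary endpoint and would appear descriptively. But 10.4.3 promises retear at each time point, and at 6 months only the under-specified model is left to provide a formal comparison.
- **The objective asks for the effect in at-risk groups, not whether it differs from other subjects.** Correct. An interaction estimate is good practice for reading such results, and its absence alone does not leave the stated objective unanswered.
- **The power figures measure the wrong thing.** They show that the groups are small, not what a missing treatment term costs, and adding the terms does not make the groups larger. This stands; the figures serve only to show how the results should be read.

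**Conclusion.** The point holds as a gap in specification. Section 10.4.3 names neither treatment nor treatment-by-factor terms, and a model with the listed terms alone cannot estimate device against control in any at-risk group. The by-arm summaries fill part of the gap but list no 6-month retear comparison, and neither route estimates how the effect varies by factor. The documents do not support the stronger readings that treatment has been deliberately left out or that the objective cannot be met. They also plan no subgroup claim; the risk of comparing separate subgroup p-values arises only if someone later makes such a claim.

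The consequence is limited to an exploratory objective. It is worth correcting but changes nothing in the primary analysis. The structural conclusion needs no assumption beyond fitting the model as listed. The precision figures rest on assumed prevalences, full evaluability and 30% against 15% in every level.

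**What to change.** State in the statistical analysis plan, for randomized subjects only and at each time point including 6 months:

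- a logistic model of retear on arm, factor and arm-by-factor, fitted for one risk factor at a time;
- the arm effect as odds ratio and risk difference with 95% CI within each level of the factor, and the interaction estimate with its CI;
- that the results are exploratory and that no subgroup claim will rest on separate p-values.

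If further covariates are wanted, name them: 10.4.1 refers to baseline characteristics without listing any, so pointing to the primary model would not define them. The restriction to randomized subjects should be explicit because revision subjects are not randomized and all receive the device (8.2.1).

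The cost is a few lines of text and model terms, with no new data. The downside is imprecision: at 20% prevalence about 26 × 0.15 = 3.9 retears would be expected in the device arm of a group, so the output supports estimation with wide intervals, not confirmation.
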